Score	Comparison								
1A	Target Plaque A is better than Target Plaque B								
0	Target Plaque A is the same as Target Plaque B								
1B	Target Plaque A is worse than Target Plaque B								

	
taken. Photographs of test sites will be taken under identical conditions, as much as possible, to enable proper comparisons to be made as detailed in the Study Photo Guide.
 
Safety:
 
Adverse Events
 
All AEs will be recorded. At each visit (except Visit 1/Screening), subjects will also be questioned specifically about the status of any ongoing AEs.
 
Brief Physical Examination
 
A brief physical exam will be performed at Visit 1/Screening and Visit 6/EOT. The exam will include examination of head and neck, dermatological, cardiovascular, respiratory, gastrointestinal (abdomen), and gross motor and gait. Abnormalities at Visit 1/Screening will be recorded as medical history. Any new or worsening abnormalities at Visit 6/EOT (and subsequent visits, if applicable) will be recorded as AEs. Directed physical exams will be performed at subsequent follow-up visits until the finding has resolved or stabilized in the opinion of the investigator.
 
Vital Signs
 
Vital signs including temperature, systolic and diastolic blood pressure, heart rate, and respiration rate will be measured at Visit 1/Screening, Visit 2/Baseline, and Visit 6/EOT. Assessments will also be performed at any subsequent follow-up visits if the results from the preceding visit are materially abnormal and clinically significant in the opinion of the investigator. Assessments will be made after the subject has rested in a seated position for at least five minutes. Height and weight will only be measured at Visit 1/Screening.
 
Clinical Laboratory Tests
 
Urine and blood samples will be collected from each subject for safety laboratory analysis at Visit 1/Screening and Visit 6/EOT. Clinical laboratory tests will also be performed at any subsequent follow-up visits if the results from the preceding visit are materially abnormal and clinically significant in the opinion of the investigator. Any new or worsening clinically significant abnormalities at Visit 6/EOT (and subsequent visits, if applicable) will be recorded as AEs.
 
Urine Pregnancy Tests
 
A UPT will be performed at Visit 1/Screening, Visit 2/Baseline, and Visit 6/EOT for WOCBP.
 
Local Skin Reactions
 
LSRs (burning/stinging, edema, and folliculitis) will be assessed at every visit (except Visit 1/Screening) using a 4-point ordinal scale (0=none, 1=mild, 2=moderate, 3=severe). Only LSRs that require medical intervention (e.g., prescription medication) will be documented as AEs. Any LSRs that are not listed above will be recorded as AEs.

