Study Endpoints	
Efficacy Endpoints:
 
For each endpoint listed below the change from Baseline will be calculated for each treatment at Visits 3, 4, 5, 6, 7, 8, and 9 and summarized. Besides

	
the change from Baseline, for each endpoint listed below, the within subject difference in the change scores between DUR-928 and VEH will also be calculated at each visit and summarized as the proportion of subjects in which DUR-928 is better than VEH, DUR-928 is the same as VEH, and DUR-928 is worse than VEH.
 
1. IGA Score.2. Clinical Signs of Psoriasis (plaque elevation, scaling, and erythema).3. LPSI (as a sum of all three parameters including plaque elevation, scaling, and erythema).4. Target Plaque Area (will only be calculated at Visits 4, 6, and 9).5. NRS for Pruritus (will only be calculated at Visits 4, 6, and 9). 
Treatment success outcomes will also be calculated and summarized as follows for each treatment at Visits 3, 4, 5, 6, 7, 8, and 9.
 
1. IGA – proportion of subjects with Target Plaques achieving a score of 0 or 1 representing “clear” or “almost clear” with at least 2-grade decrease in severity relative to Baseline.2. Clinical Signs of Psoriasis – for each clinical sign (plaque elevation, scaling, erythema) the proportion of subjects with Target Plaques achieving a score of 0 or 1 representing “clear” or “almost clear” with at least 2-grade decrease in severity relative to Baseline.3. NRS for Pruritus – proportion of subjects with Target Plaques that have a Baseline NRS score ≥ 4 and at least a 4 point decrease in NRS score relative to Baseline (will only be calculated at Visits 4, 6, and 9).4. Target Plaque Area – proportion of subjects with Target Plaques achieving a 50% reduction in Target Plaque Area from Baseline (will only be calculated at Visits 4, 6, and 9). 
Additionally, Target Plaque Comparison score results will be summarized at Visits 2, 3, 4, 5, 6, 7, 8, and 9 as the proportion of subjects with each score including, 1A = Target Plaque A is better than Target Plaque B, 0 = Target Plaque A is the same as Target Plaque B, and 1B = Target Plaque A is worse than Target Plaque B.
 
Safety Endpoints:
 
1. Incidence (severity and causality) of any local and systemic AEs.2. Number of subjects with presence (and severity) of the following LSRs: burning/stinging, edema, and folliculitis at each time point (except Screening).3. Changes from Baseline in vital signs at Visit 6/EOT (and subsequent visits, if applicable).4. Changes from Screening in clinical laboratory tests (chemistry, hematology, and urinalysis) at Visit 6/EOT (and subsequent visits, if applicable). 
Photography
 
Photographs taken by the sites only shall be used as supportive documentation of efficacy and safety outcomes for this study. An independent photo review may be performed at the discretion of the Sponsor.

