To minimize errors, at each clinic visit during the treatment period the site must review and emphasize the proper application of the test article.

Subjects will be provided with a Subject Instruction Sheet detailing how to apply the test articles and perform occlusion ([CC1]) and a Subject Diary ([CC1]) to record dates and times of applications and occlusion. Subjects will be instructed to bring all test article containers (used and unused) and the Subject Diary to the study visits. At the appropriate study visits, Subject Diary will be collected, reviewed, and a new one will be dispensed to the subject (as needed). Subjects will be instructed to store the test articles according to the directions on the label.

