10.1 Efficacy Evaluations

10.1.1 *Investigator's Global Assessment*

The IGA score is a static evaluation of the overall or “average” degree of severity of each of the two Target Plaques by the investigator or designee as the subject appears on the day of evaluation. This evaluation takes into consideration the three individual characteristics of psoriasis (plaque elevation, scaling, and erythema) with the IGA score at each visit representing the average of plaque elevation, scaling, or erythema that is present amongst

the two Target Plaques. IGA will be assessed individually for the two Target Plaques on a 5-point scale where 0 = clear, 1 = almost clear, 2 = mild, 3 = moderate, and 4 = severe.

The investigator should NOT refer to any other assessments to assist with this evaluation. This evaluation is NOT a comparison with the IGA at any other visit or a mathematical calculation based on the clinical signs of psoriasis scores. The Visit 2 assessment must be made PRIOR to the first application of the test articles and subsequent assessments should be made four hours or more after any application of the test article.

At every study visit, both Target Plaques will be evaluated individually and the one whole integer score will be documented that describes the average IGA for each Target Plaque using the following scale:

CLEAR (0)
Scaling: no evidence of scaling
Erythema: no evidence of erythema (except possible residual discoloration)
Plaque Elevation: no evidence of plaque elevation above normal skin level

ALMOST CLEAR (1)
Scaling: limited amount of very fine scale
Erythema: light pink color dominates over all or part of the plaque
Plaque Elevation: very slight elevation above normal skin level, easier felt than seen

MILD (2)
Scaling: mainly fine scales; plaque is partially covered
Erythema: light red to pink dominates over all or part of the plaque
Plaque Elevation: slight but definite elevation above normal skin level, typically with edges that are indistinct or sloped over most of the plaque

MODERATE (3)
Scaling: somewhat coarser scales; a significant portion or all of the plaque is covered
Erythema: red dominates over all or part of the plaque
Plaque Elevation: moderate elevation with rounded or sloped edges on most of the edges of the plaque

SEVERE (4)

Scaling: coarse, thick scales; virtually all of the plaque is covered; rough surface
Erythema: virtually all of the plaque is bright to dusky red

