10.2 Safety Evaluations

10.2.1 *Brief Physical Examination*

A brief physical exam will be performed at Visit 1/Screening and Visit 6/EOT. The exam will include examination of head and neck, dermatological, cardiovascular, respiratory, gastrointestinal (abdomen), and gross motor and gait. Abnormalities at Visit 1/Screening will be recorded as medical history. Any new or worsening abnormalities at Visit 6/EOT (and subsequent visits, if applicable) will be recorded as AEs. Directed physical exams will be performed at subsequent follow-up visits until the finding has resolved or stabilized in the opinion of the investigator.

10.2.2 *Vital Signs*

Vital signs including temperature, systolic and diastolic blood pressure, heart rate, and respiration rate will be measured at Visit 1/Screening, Visit 2/Baseline, and Visit 6/EOT. Assessments will also be performed at any subsequent follow-up visits if the results from the preceding visit are materially abnormal and clinically significant in the opinion of the investigator. Assessments will be made after the subject has rested in a seated position for at least five minutes. Height and weight will only be measured at Visit 1/Screening.

10.2.3 *Local Skin Reactions*

LSRs (burning/stinging, edema, and folliculitis) will be assessed for each Target Plaque at every visit (except Screening) using a 4-point ordinal scale (0=none, 1=mild, 2=moderate, 3=severe). Only LSRs that require medical intervention (e.g., prescription medication) will be documented as AEs. Any LSRs that are not listed above will be recorded as AEs.

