17.3.2 Safety Endpoints

1. Incidence (severity and causality) of any local and systemic AEs.
2. Number of subjects with presence (and severity) of the following LSRs: burning/stinging, edema, and folliculitis at each time point (except Screening).
3. Changes from Baseline in vital signs at Visit 6/EOT and subsequent visits (if applicable).
4. Changes from Screening in clinical laboratory tests (chemistry, hematology, and urinalysis) at Visit 6/EOT and subsequent visits (if applicable).

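### Listed local skin reactions have no look-back period, so untreated reactions that clear between visits reach no described dataset and absolute rates are likely understated

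*Combined protocol and SAP*

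**What the plan says.** Burning/stinging, edema and folliculitis are the three listed local skin reactions (LSRs). The synopsis (Study Measurements, Safety) states: "LSRs (burning/stinging, edema, and folliculitis) will be assessed at every visit (except Visit 1/Screening) using a 4-point ordinal scale". Section 10.2.3 gives the same rule by plaque: they "will be assessed for each Target Plaque at every visit (except Screening) using a 4-point ordinal scale". Neither place says whether the score covers the moment of the visit or the interval since the last one.

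Safety endpoint 2 in section 17.3.2 is the "Number of subjects with presence (and severity) of the following LSRs: burning/stinging, edema, and folliculitis at each time point (except Screening". Section 17.4.2 plans a frequency summary of each LSR by treatment group, in the Safety population. No any-time incidence or worst post-baseline grade is planned.

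The AE rule in section 10.2.3 has two parts: "Only LSRs that require medical intervention (e.g., prescription medication) will be documented as AEs", but "Any LSRs that are not listed above will be recorded as AEs".

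Section 9.3 adds one score 15 minutes after the first application, with occlusion delayed until it is done. Section 6.2 describes the Subject Diary as a place "to record dates and times of applications and occlusion"; the form itself is redacted. Under section 11, the daily home photographs support compliance review only and are not collected.

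**The concern.** Treatment is once daily for four weeks, and the text places only the first application under site supervision. Most exposure, including the roughly two-hour occlusion, therefore happens at home. A listed reaction that starts and resolves at home may be absent at the next visit. The usual fallback, an AE report, is closed to it unless it needed medical intervention. The expected reactions thus have weaker between-visit capture than unexpected ones, which are always AEs.

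Comparing tolerability with vehicle is part of the primary objective in section 3. If the LSR table shows what was present on a few weekly visit days, a reader of the results could take it as the share of subjects who had a reaction.

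**Working it through.** The plan states no LSR rate, duration or power, so there is no figure to reproduce. The check has two parts.

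**1. Where could an untreated, listed, between-visit reaction be recorded?**

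- *LSR score, Visits 3 to 6:* only if still present, or if the site chooses to ask about the interval.
- *15-minute score (section 9.3):* covers 1 of about 4 × 7 = 28 applications, and comes before occlusion. So 0 of about 28 applications have a timed LSR score during or just after occlusion.
- *AE data:* the question about health changes since the previous visit (section 14.2) may elicit the reaction, but the LSR rule keeps it out if untreated.
- *Diary:* its stated purpose is dosing and occlusion times, and no endpoint draws on a symptom item.
- *Home photographs:* not collected.
- *Instruction to stop and make contact if irritation develops (section 6.3):* can leave a missed dose or a withdrawal, but no reaction type, grade or plaque.

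**2. How much could be missed?**

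Inputs from the protocol are visits on nominal Days 8, 15, 22 and 29 and about 20 enrolled subjects. Assumptions, not in the documents: one isolated episode per affected subject, onset uniform over 28 days, duration d days, and a score that reflects only what is present at the visit.

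Each visit catches onsets in the d days before it, so P(seen) = 4d/28 = d/7, capped at 1:

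- d = 1: 1/7 = 14%
- d = 2: 2/7 = 29%
- d = 3: 3/7 = 43%
- d = 7: 100%
- 2, 6 or 12 hours: 1%, 4% or 7%

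Now let visits fall evenly on whole days within their windows (±1, ±2, ±2, +3). For d up to 3, P(seen) = [3d + mean of max(d − j, 0) over j = 0, 1, 2, 3]/28:

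- d = 1: (3 + 0.25)/28 = 12%
- d = 2: (6 + 0.75)/28 = 24%
- d = 3: (9 + 1.5)/28 = 38%
- d = 7, by simulation: 88%

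If 6 of 20 subjects (assumed) each have one episode, at nominal visit days:

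- d = 1: expected seen 6 × 1/7 = 0.9; chance that none is seen (6/7)^6 = 40%
- d = 2: 6 × 2/7 = 1.7; (5/7)^6 = 13%
- d = 3: 6 × 3/7 = 2.6; (4/7)^6 = 3.5%

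Repeat episodes raise detection. With four independent episodes, 1 − (1 − d/7)^4 = 46%, 74% and 89% for d = 1, 2 and 3.

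*Effect on the comparison.* If a share c of episodes is seen on either plaque, the observed difference is c × (p₁ − p₀), while the ratio stays p₁/p₀. With assumed incidences of 40% and 10% and d = 2, 30 points × 2/7 = 8.6 points. In 20 subjects, 8 and 2 affected become 8 × 2/7 = 2.3 and 2 × 2/7 = 0.6, still 4 to 1.

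**The case against.** The strongest reply is that the defect is an undefined assessment period, not a proven loss. The IGA and clinical-sign sections say the grade describes the subject on the day of evaluation, and the LSR section does not. Burning and stinging are symptoms the subject must report, so a site could reasonably ask about the past week. This stands in part. The words on each time point favour a same-day reading without settling it. The pruritus scale in section 10.1.5, however, states a 24-hour look-back, so the protocol writes one when it wants one. If sites are free to choose, about three sites may score differently, and the same clarification is needed.

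A reader might infer that these reactions are recorded nowhere. The documents do not support that. The diary form is redacted, subjects are questioned at each visit, stopping for irritation can leave a trace in dosing or disposition data, and unlisted reactions are always AEs. What can be said is that no described dataset or analysis holds the reaction with its type, grade and plaque.

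A reader might also infer that stinging that fades within hours is never seen, because "subsequent assessments should be made four hours or more after any application of the test article". That rule is stated for the IGA, with a matching one for the clinical signs in section 10.1.3, and not for LSRs. The timing of LSR scores relative to dosing after Visit 2 is simply not given.

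Finally, the rates and durations above are assumed, LSRs are only described and not tested, and the study is a pilot. All of this is correct and limits the weight of the point.

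**Conclusion.** The point holds as a gap in ascertainment. With no look-back period and with untreated listed reactions kept out of the AE data, a short reaction between visits reaches no described dataset or analysis. Absolute LSR incidence is likely understated and the difference between treatments attenuated.

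The size depends on duration and recurrence, which the documents do not give. It is large for isolated reactions of one to three days (roughly 57% to 86% missed at nominal visit days) and small for week-long ones. Reactions that recur are seen more often. If sites already ask about the whole interval, most of the loss disappears.

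A reader might conclude that tolerability will be shown as better than it is, or that the comparison favours DUR-928. The first is a plausible direction for absolute rates, not a demonstrated result. The second is not supported: both plaques in a subject share the same visits and rules, so the ratio is not expected to be biased, provided episodes last about as long on either plaque.

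This is a cheap improvement, not a flaw that invalidates the design.

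**What to change.** In the synopsis and section 10.2.3, at Visits 3 to 7, score each listed LSR per Target Plaque on the existing 0–3 scale twice: *present now*, and *worst since the previous visit*, asked of the subject. Visit 7 picks up reactions to the last doses that appear after Visit 6.

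Add to safety endpoint 2, in the Safety population and by treatment, the number of subjects with any listed LSR since first dose and the worst post-baseline grade. Keep the by-visit summary, labelled as presence at the visit. The AE rule stays as it is.

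The cost is one extra eCRF field per reaction and plaque at five existing visits (3 × 2 = 6 fields per visit) and one summary table. No extra visit or procedure is needed. The downside is recall over about a week, and at most 12 days if Visit 5 falls on Day 20 and Visit 6 on Day 32.

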CCI

Product Name: DUR-928 Topical Solution
Sponsor Name: Therapeutics, Inc.

Protocol: C928-015
Protocol Date: May 22, 2019, v4.0

C [REDACTED]

[REDACTED]

[REDACTED]

[REDACTED]

[REDACTED]

I [REDACTED]

[REDACTED]

3. OBJECTIVE

The primary objective of this trial is to determine and compare the safety, tolerability, and efficacy of DUR-928 with that of the vehicle control in subjects with plaque psoriasis with occlusion.

4. STUDY DESIGN

This is a multicenter, randomized, double-blind, vehicle-controlled, paired-plaque, proof of concept comparison study of DUR-928 in subjects with stable mild to moderate plaque psoriasis. Eligible subjects must have two similar contralateral Target Plaques as described in [Section 5.1.1](#). Approximately 20 subjects will be enrolled at approximately three study sites to obtain about 15 evaluable subjects. The maximum proportion of subjects to be enrolled with mild plaque psoriasis is approximately 25% of the total enrolled subjects.

Each subject will receive both of the following treatments with occlusion:

1. DUR-928 Topical Solution,  and
2. Vehicle Topical Solution

Subjects will be instructed to apply the test articles once daily to the two Target Plaques at approximately the same time and follow the instructions for application and occlusion. Subjects will be allowed to use triamcinolone cream, 0.1% and/or over the counter (OTC) hydrocortisone ointment or cream 1% or 0.5% on the face/neck, trunk, buttocks, and lower extremities only no more than twice daily. Subjects will also be allowed to use a bland emollient on all areas (face/neck, trunk, buttocks, lower extremities, upper extremities) that are not designated Target Plaques no more than twice daily. There will be nine study visits. Efficacy will be measured through Investigator's Global Assessment (IGA), Clinical Signs and Symptoms of Psoriasis including Local Psoriasis Severity Index (LPSI), Target Plaque Area, and Target Plaque Comparison assessments by the investigator or designee in a blinded fashion. Efficacy will also be measured using the subject-assessed Numeric Rating Scale (NRS) for Pruritus. Safety will be measured by brief physical examinations, vital signs, clinical laboratory tests, urine pregnancy tests (UPTs, if applicable), local skin reactions (LSRs), and adverse events (AEs).

5. STUDY POPULATION

5.1 Subject Eligibility

To be included in the study, subjects must meet the following inclusion and none of the exclusion criteria.

5.1.1 Inclusion Criteria

1. Subject is a male or non-pregnant female 18 years of age or older.
2. Subject has provided written informed consent.

3. Subject has a clinical diagnosis of stable mild to moderate plaque psoriasis for at least two months.
4. Females must be post-menopausal⁶, surgically sterile⁷, or use an effective method of birth control.^{8,9} Women of childbearing potential (WOCBP) must have a negative UPT¹⁰ at Visit 2/Baseline.
5. Males (or their female partner) must agree to use an effective method of birth control throughout the study.
6. Subject has two similar contralateral Target Plaques that:
 - Are located on the upper extremities not including the palms, and
 - Must individually be a minimum of 6 cm² in area, a maximum of 64 cm² in area, and a similar size (both Target Plaques should ideally be the same size but one should not be more than about a third larger [e.g., 33%] than the smaller plaque), and
 - Must have the same IGA score of 2 or 3, and
 - Must have the same plaque elevation score of 2 or 3, and
 - Have a Target Plaque Comparison score of 0 (Target Plaque A=Target Plaque B), and
 - Are easily accessible for test article application by the subject or a reliable care provider.
7. Subject is willing and able to apply the test article(s) as directed, comply with study instructions, and commit to all follow-up visits for the duration of the study.
8. Subject, in the investigator's opinion, is in good general health and free of any disease state or physical condition that might impair evaluation of the plaque psoriasis or exposes the subject to an unacceptable risk by study participation.

5.1.2 Exclusion Criteria

1. Subject is pregnant, lactating, or is planning to become pregnant during the study.
2. Subject has spontaneously improving or rapidly deteriorating plaque psoriasis.

⁶ Defined as amenorrhea greater than 12 consecutive months in women 50 years of age and older.

⁷ Hysterectomy, bilateral tubal ligation (at least six months prior to initiation of treatment), or bilateral oophorectomy.

⁸ Effective forms of birth control include a) hormonal contraceptives [e.g., oral, transdermal, injectable, implantable, or vaginal ring] (see next footnote), b) intrauterine device (IUD) for at least one week prior to test article application, c) barrier methods [condom and spermicidal or diaphragm/cervical cap and spermicidal], d) monogamous relationship with a partner who is sterile [e.g., vasectomy performed at least six months prior to study entry], or e) total abstinence for subjects who are not sexually active. Subjects who become sexually active or begin to have relations with a partner who is not sterile during the study must agree to use an effective form of birth control for the duration of the study.

⁹ WOCBP taking hormonal therapy must be on treatment prior to study entry, continued per label, and must not change their dosing regimen during the study; treatment must be for (1) oral: at least one complete cycle (e.g., four to eight weeks); (2) transdermal, injectable (e.g., Depo-Provera), implantable, or vaginal ring (e.g., NuvaRing): at least one week.

¹⁰ UPT must have a minimum sensitivity of 25 mIU β-hCG/mL.

3. Subject has guttate, pustular, erythrodermic, inverse, or other non-plaque forms of psoriasis.
4. Subject has any skin pathology or condition that, in the investigator's opinion, could interfere with the evaluation of the test article or requires use of interfering topical, systemic, or surgical therapy.
5. Subject has psoriasis beyond the two Target Plaques that, in the investigator's opinion, could not be reasonably managed with only bland emollient, triamcinolone cream, 0.1%, or OTC hydrocortisone during the study.
6. Subject has used any systemic methotrexate, retinoids, systemic corticosteroids (including intralesional, intra-articular, and intramuscular corticosteroids), cyclosporine, tofacitinib, apremilast, or analogous products within 90 days prior to Visit 2/Baseline.
7. Subject has used any systemic immunomodulatory biologic therapy (i.e., FDA-approved or experimental therapy) within five half-lives of the biologic prior to Visit 2/Baseline. Published or documented half-life of the product provided by the commercial supplier or Sponsor should be used to establish this value.
8. Subject has used any phototherapy (including laser), photo-chemotherapy, or other forms of photo-based therapy for the treatment of their psoriasis within 30 days prior to Visit 2/Baseline.
9. Subject had prolonged exposure to natural or artificial sources of ultraviolet radiation within 30 days prior to Visit 2/Baseline or is intending to have such exposure during the study which, in the opinion of the investigator, is thought to modify the subject's disease.
10. Subject has used topical body (excluding the scalp) psoriasis therapy (including coal tar, anthralin, steroids, retinoids, and vitamin D analogs) within 14 days prior to Visit 2/Baseline.
11. Subject has undergone treatment with Vitamin A supplements within 14 days prior to Visit 2/Baseline.
12. Subject has used emollients/moisturizers on areas to be treated within four hours prior to clinical evaluation at Visit 2/Baseline.
13. Subject is currently using lithium or Plaquenil (hydroxychloroquine).
14. Subject is currently using a beta-blocking medication (e.g., propranolol) or angiotensin converting enzyme (ACE) inhibitor at a dose that has not been stabilized (i.e., on the same dosage for at least four weeks).
15. Subject has a history of cancer, with the exception of successfully treated non-metastatic basal cell and squamous cell carcinoma.
16. Subject is currently enrolled in an investigational drug or device study.
17. Subject has used an investigational drug or investigational device treatment within 30 days prior to Visit 2/Baseline.
18. Subject has been previously enrolled in this study and treated with test article.
19. Subject has a history of sensitivity to any of the ingredients in the test articles.
20. Subject is known to be noncompliant or is unlikely to comply with the requirements of the study protocol (e.g., due to alcoholism, drug dependency, mental incapacity) in the opinion of the investigator.

